Official Title of the study:

Fibrinolysis Compared to Thoracoscopy for
Pleural Infection

NCT number:

NCT03468933

Date of the document:

July 1, 2017

Patient Population

Subjects (> 18 years of age) with either CPPE or empyema will be screened for inclusion. Screening logs recording reasons for non-trial entry will be kept.

CPPE is defined as non-purulent effusions in a patient with clinical evidence of infection such as fever and/or elevated blood leukocyte count and/or elevated CRP, with pleural fluid pH ≤ 7.2 (measured by blood-gas analyzer), or pleural fluid glucose < 60 mg/dl or pleural fluid LDH >1000 IU/L. Empyema is defined as pus within the pleural space and/or presence of bacteria on pleural fluid Gram stain or culture.

For patients to be considered for the trial they need to fulfill one of the following criteria: 1) CPPE along with evidence of septated pleural effusion on pleural ultrasonography and/or chest CT scan ²⁶ (Figure 1) with entrapped lung or 2) empyema.

[figure not shown]

Figure 1. Thoracic ultrasound showing complex pleural effusion along with septation (arrowhead)

Study exclusion criteria are: 1) age <18 years; 2) pregnant women 3) inability to give informed written consent; 4) previous thoracic surgery or thrombolytic therapy for pleural infection; 5) medical thoracoscopy cannot be performed within 48 hours; 6) inability to tolerate procedure due to hemodynamic instability or severe hypoxemia; 7) unable to correct coagulopathy, 8) presence of a homogeneously echogenic effusion on pleural US²⁶ (Figure 2) and 9) evidence of non-expandable lung (air in pleural space) after initial thoracentesis or small bore chest tube on chest CT imaging.

Figure 2. Thoracic ultrasound showing homogeneously echogenic loculated effusion

All patients will undergo diagnostic thoracentesis and chest computed tomography as part of routine care, prior to the enrollment in the study. Women of childbearing potential will have a pregnancy test as part of standard of care and pregnant women will be excluded from the study. Intravenous antibiotics will be changed to oral consolidation therapy by the managing consultant in light of the clinical response. Antibiotic therapy will be continued between 2 and 6 weeks, as required.

Patients who accept to be involved in the trial will sign an informed consent and then will be randomized to either Medical Thoracoscopy (Treatment Arm) or Fibrinolytic Therapy (Control Arm). (Figure 3)

Chest computed tomography (CT) will be done prior to randomization (day 0), prior to chest tube removal and at 12 weeks follow up visit respectively as part of standard of care protocol. On chest CT without contrast, pleural effusion will be defined as loculated if it had (1) lobulated shape with a convex border or (2) compartmentalized, accumulated in a fissure or a non-dependent portion of the pleura. On chest ultrasound pleural effusion will be defined as fibrin strands or septa floating inside the anechoic/hypoechoic pleural effusions along with presence of defined multiple pockets in the pleural cavity²⁷

Operative Technique

I-Medical Thoracoscopy (Thoracoscopy Arm)

Patients will undergo medical thoracoscopy (rigid or semi-rigid) within 48 hours of randomization. Under ultrasound guidance, a single port (with a maximum of 2 ports) will be placed and thoracoscopy will be performed under moderate sedation in the operating room or endoscopy suite with continuous monitoring as per standard protocols, with the patient in a lateral decubitus position. The pleura will be carefully inspected through the thoracoscope under direct visualization. With the closed biopsy forceps, step by step, fibrinous septate will be disrupted with fluid and fibrinopurulent material aspirated and removed from the pleural cavity. A suction irrigator device) will be used at the discretion of the operator. Following adhesiolysis, a pleural lavage with a liter of warmed saline will be done. At the end of the procedure, a drain

(24Fr) will be inserted and connected to underwater seal suction with a negative pressure suction of 20 cm H₂O. A chest CT without contrast will be performed and if there was no evidence of significant residual pleural effusion and chest tube drainage is <75ml/day the chest drain will be removed. The fluid volume will be calculated by measuring the maximum perpendicular distance between the surface and the chest wall right above the diaphragm with at maximum inspiration in the most dependent position.²⁸

II-Fibrinolytic Therapy (Fibrinolytic Arm)

A chest tube (14-French Seldinger or less) under ultrasonography guidance will be inserted into the most dependent area of the pleural effusion or into the largest loculation in patients with multiloculated effusions. The dose of DNase (Pulmozyme, Genentech, USA) is 5 mg and the dose of tPA (Actilyse, Genentech, USA) is 10 mg, each in 50 ml of 0.9% NaCl. tPA and DNase will not be mixed together in one syringe. Concurrent tPA and DNase will be administered intrapleurally through the chest tube followed by 60 ml saline flush. The tube will then be clamped for 120 minutes before the chest tube will be opened to -20 cmH₂O of wall suction. Therapy will be given twice daily for a maximum of 6 doses. A chest CT without contrast will be performed and if there was no evidence of significant pleural effusion²⁸ and chest tube drainage is <75 ml/day, the catheter will be removed.

Study Outcome

Primary outcome measure:

- Duration of hospital stay after intervention

Secondary outcome measures:

- Total length of hospital stay
- Failure rate of assigned treatment (persistent fever, leukocytosis evidence of loculation 48 hours post intervention) necessitating intervention defined as any of the following:
 - 1-Surgical intervention (VATS, open thoracotomy) in the medical thoracoscopy or fibrinolytic therapy arm
 - 2-Need of additional chest tube and/or fibrinolytic therapy in the medical thoracoscopy arm due to clinical non-responsiveness
 - 3-Need of additional chest tube in the fibrinolytic therapy arm due to clinical non-responsiveness
- Adverse events
 - Pleural bleeding defined as drop in serum hematocrit requiring blood transfusion or causing hemodynamic instability
 - Significant pain requiring escalation of analgesia
- In hospital and 30 day mortality

[figure not shown]

Figure 3. Proposed Study Protocol

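### Can the same lung finding both admit a CPPE patient and exclude that patient?

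*Protocol*

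**What the plan says.** All the relevant text is in the Protocol, almost all of it under Patient Population.

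- **Entry.** The section opens the entry rule with "For patients to be considered for the trial they need to fulfill one of the following criteria" and gives two alternatives. The first is CPPE with "evidence of septated pleural effusion on pleural ultrasonography and/or chest CT scan", plus a further condition on the lung: "Figure 1) with entrapped lung or 2) empyema". The second, empyema, carries no lung condition.
- **Exclusion 9.** It removes patients with "evidence of non-expandable lung (air in pleural space) after initial thoracentesis or small bore chest tube on chest CT imaging".
- **Timing.** The same section says "All patients will undergo diagnostic thoracentesis and chest computed tomography as part of routine care, prior to the enrollment in the study". The imaging paragraph before Operative Technique adds "Chest computed tomography (CT) will be done prior to randomization (day 0".
- **Definitions.** CPPE, empyema and loculation on CT are each defined, and an ultrasound description is given. Entrapped lung is not defined, and nothing says how it differs from the finding in exclusion 9.
- **Records.** A screening log with the reasons for non-entry is required.

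**The concern.** In ordinary language an entrapped lung and a non-expandable lung are close relatives: both describe a lung that does not fill the chest because something in the pleural space prevents it. The Protocol makes the first a condition of entry for CPPE and the second a reason for exclusion, and both can be judged on the same work-up before enrolment. A reader who treats the two terms as synonyms concludes that every CPPE patient who meets the inclusion line also meets exclusion 9.

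If that were so, the CPPE route would be empty, or would depend on which label a screener happened to write down. The trial would then recruit mainly or only empyema, and its result would not speak to the CPPE-or-empyema population that the Protocol describes. With so few patients planned, even a handful of inconsistent decisions would visibly alter the mix.

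**Working it through.** The documents state no figure on this point, so the check is a comparison of the two criteria, followed by a note on scale.

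**Step 1: the criteria side by side.**

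| Feature | CPPE inclusion | Exclusion 9 |
|---|---|---|
| Term | entrapped lung | non-expandable lung |
| Marker | none given | air in the pleural space |
| Time | none given | after thoracentesis or small-bore tube |
| Test | ultrasound and/or CT for the septation; none given for entrapment | chest CT |

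The documents never equate the two terms. Exclusion 9 is the more tightly specified of the two.

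**Step 2: each type of patient under the text as printed.**

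| Patient | Meets inclusion? | Caught by exclusion 9? | Result |
|---|---|---|---|
| Septated CPPE, entrapped lung, no pleural air | yes | no | eligible |
| Septated CPPE, pleural air on CT after drainage | depends on how entrapped is read | yes | excluded either way |
| Septated CPPE, lung not entrapped | no | not needed | not eligible |
| Empyema, no pleural air | yes | no | eligible |
| Empyema, pleural air on CT after drainage | yes | yes | excluded |

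Every row has one result. The first row shows that the CPPE route is open. The second is the only place where one finding could be said to meet both criteria, and there the result does not depend on how the inclusion term is read.

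**Step 3: what it would take to close the route.** Three readings are needed together:

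1. The words about pleural air are treated as an incidental remark, not as the sign to look for.
2. Entrapped is taken to mean the same as non-expandable.
3. Entrapment is judged on a CT taken after drainage.

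The first sets aside printed words. The second is an inference. The third is not stated: the Protocol puts thoracentesis and CT before enrolment but does not give their order. If any one of the three fails, some CPPE patients can enter. A site is also unlikely to adopt a reading that makes one of its two entry routes pointless.

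**Step 4: effect on the comparison.** Eligibility is decided first; consent and randomisation follow. A screener who reads entrapped broadly or narrowly therefore alters who enters the trial, not which arm they join. In expectation the CPPE-to-empyema mix is the same in both arms.

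**Step 5: scale.** The SAP plans 16 patients per group, so 2 × 16 = 32 in total. One patient admitted or refused on a debatable reading is 1/32 = 3.1% of the trial, or 1/16 = 6.3% of an arm. The SAP derives its sample size from a 2-day difference in post-intervention stay, with a two-sided type I error of 0.05 and 80% power. The CPPE share does not enter that calculation.

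**The case for a change.** The best case for a change is this. A condition of entry is left undefined in a section that takes care to define CPPE and empyema. The mention of pleural air in exclusion 9 could be an example of non-expandable lung, not its definition, and nothing in the inclusion line mirrors it. The septation may be seen on ultrasound, but every patient also has a CT, so exclusion 9 can always come into play. Because only CPPE carries the lung condition, inconsistent screening acts on one route alone and shifts the mix. Similar patients might also be logged under different reasons, which weakens the account of who was studied. A clarifying sentence would cost almost nothing.

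Much of this stands. The term is undefined, two screeners could disagree about a particular CPPE patient, and the description of the enrolled population could be less crisp as a result.

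What does not stand is the step from an undefined term to a contradiction, or to a trial of empyema alone. That step needs all three readings in Step 3, and the documents give no figure to support such a drift. The obvious remedies also add little or go too far. Limiting exclusion 9 to pleural air after drainage would largely restate what it already says. Removing the entrapment condition would alter the eligible population, which is a clinical choice for the investigators and not a tidying of the text. The required screening log already offers a way to see how many patients were turned away under exclusion 9.

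**Conclusion.** The concern does not hold as a contradiction, and no change to the plan follows. The two criteria overlap at most for CPPE patients with pleural air on CT after drainage, and those patients are excluded on any reading. What is left is a missing definition, of a kind that screening clinicians normally settle by judgement when they apply the criteria.

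The number of patients affected cannot be derived, because the documents give neither the CPPE share nor the frequency of pleural air after drainage. Each disputed case is about 3% of the planned 32. The consequence is confined to how precisely the enrolled population can be described. The between-arm comparison, the sample size and the tests in the SAP do not depend on it.

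This rests on two assumptions. The first is that exclusion 9 is applied to imaging obtained before randomisation, as the stated timing of thoracentesis and CT indicates, and is not used to remove patients after their assigned treatment has begun. The second is that the mention of pleural air is read as the sign that triggers the exclusion. If it were read only as an example, the zone of disagreement would widen and the CPPE route could narrow, but it would still not close unless the other two readings in Step 3 were adopted as well. The Protocol's study-scheme figure is not available in the text reviewed, so it is not known whether it clarifies the terms further.

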Official Title of the study:

Fibrinolysis Compared to Thoracoscopy for Pleural Infection

NCT number:

NCT03468933

Date of the document:

July 1, 2017

Statistical Analysis

We believe that a difference of 2 days in the length of the postintervention hospital stay between the two treatment arms would be clinically important. This rationale is based on a previous randomized study that compared VATS and streptokinase therapy in empyema (1). In that study, the number of chest tube days after VATS was 5.8 ± 1.1 days, as compared with 9.8 ± 1.3 days in the streptokinase group. Furthermore, a case series from MT trials reported an average postoperative stay of 7–8 days (2-5), as compared with an average of 10–13 days in IPFT trials (6,7). According to a two-sided type I error of 0.05 and 80% power, the sample size was 16 patients in each group.

All analyses were performed using GraphPad Prism (version 7.0; GraphPad Software). Descriptive statistics were used to summarize the patients' characteristics. The t test was used to examine differences between groups with parametric data and the Mann-Whitney U test was used for nonparametric data. Fisher's exact test was used for categorical variables. A P value of <0.05 was considered statistically significant.

- 2-BrutscheMH, Tassi GF,Gyo" rik S,Go" keimenM, Renard C,MarchettiGP, et al. Treatment of sonographically stratified multiloculated thoracic empyema by medical thoracoscopy. Chest 2005;128:3303–3309.
- 4-Sole`r M, Wyser C, Bolliger CT, Perruchoud AP. Treatment of early parapneumonic empyema by "medical" thoracoscopy. Schweiz Med Wochenschr 1997;127:1748–1753.

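### Total hospital stay, a secondary outcome, is undefined and compared unadjusted; days before randomisation may cost it precision, though they cause no bias

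*Protocol*

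**What the plan says.** The protocol (Study Outcome) sets the primary outcome as "Duration of hospital stay after intervention" and lists "Total length of hospital stay" separately as the first secondary outcome. It gives no start or end point for the second.

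Under Patient Population it states: "All patients will undergo diagnostic thoracentesis and chest computed tomography as part of routine care, prior to the enrollment in the study". Consent and randomisation follow, and randomisation is labelled day 0. None of the nine exclusions limits earlier hospital days or removes patients already admitted for another reason. The ninth allows that a patient may have had a small drain before entry. Under Operative Technique, "Patients will undergo medical thoracoscopy (rigid or semi-rigid) within 48 hours of randomization"; no matching window is given for the fibrinolytic arm.

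The SAP (Statistical Analysis) says "The t test was used to examine differences between groups with parametric data", and in the same sentence assigns the Mann-Whitney U test to nonparametric data. It names no covariate and no regression model. Its sample size rests on "a difference of 2 days in the length of the postintervention hospital stay between the two treatment arms would be clinically important", so it was set for the primary outcome.

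**The concern.** Beside a primary outcome that starts at the intervention, a total stay most naturally means admission to discharge. It is then the sum of two parts: days already spent when the patient is randomised, and days that assignment can influence. The first part carries no treatment effect. An unadjusted test leaves its variance in the error term, although its value is known for every patient at entry.

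With 16 patients per arm there is little room for avoidable noise. Total stay is also the only listed outcome that counts the wait between randomisation and intervention, which assignment can affect and the primary omits. A blurred comparison here would lose information that the primary does not supply.

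**Working it through.** **Inputs from the SAP.** Difference 2 days, two-sided 0.05, 80% power, 16 per group.

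**Inputs the documents do not give.** The SD of hospital stay; the SD of pre-randomisation days; the correlation (ρ) between the two parts. These are assumptions below.

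**1. Reproducing 16 per group.** n = 2(1.960 + 0.842)² × SD² / 2². With SD 2.0 this is 2 × 7.85 × 4/4 = 15.7, so 16. Solving backwards from 16 gives SD = 2 / (2.802 × √(2/16)) = 2.02 days (normal approximation), or 1.95 with the t distribution. The SAP's only SDs, 1.1 and 1.3, are for chest-tube days and would give 5 to 7 per group (6 to 8 with t). The figure 1.95 is therefore inferred, not stated. It is used here as SDpost, the SD of days after randomisation.

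**2. Unadjusted total stay.** Total = pre + post, so

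SD(total) = √(SDpre² + SDpost² + 2ρ × SDpre × SDpost).

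Take ρ = 0 first. At SDpre = 2, SD(total) = √(3.80 + 4) = 2.79. The noncentrality is (2/2.79) × √(16/2) = 2.03 on 30 df, which gives 50% power. The 95% CI half-width is 2.042 × SD(total) × √(2/16).

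| SDpre (days) | SD(total) | t-test power | CI half-width (days) | Mann-Whitney power | Adjusted power, raw scale |
|---|---|---|---|---|---|
| 0 | 1.95 | 80% | 1.41 | – | – |
| 0.5 | 2.01 | 78% | 1.45 | – | – |
| 1 | 2.19 | 70% | 1.58 | 67% | 79% |
| 2 | 2.79 | 50% | 2.02 | 50% | 78% |
| 3 | 3.58 | 33% | 2.58 | 40% | 79% |
| 4 | 4.45 | 23% | 3.21 | 34% | 78% |

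The t-test column is the noncentral-t calculation. The last two columns are simulated with skewed (gamma, mean 3) pre-randomisation days and carry an error of a point or two. With the same skewed days, the t test simulated at 50, 35 and 27% for SDpre 2, 3 and 4.

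**3. Adjusted total stay.** With arm and pre-randomisation days in a linear model, the residual SD is SDpost × √(1 − ρ²). SDpre drops out, which is why the last column is flat.

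**4. Correlation.**
- ρ = −0.5, SDpre = 1: SD(total) = √(3.80 + 1 − 1.95) = 1.69, and the adjusted SD is 1.95 × √0.75 = 1.69. Power is about 90% either way, so nothing is gained.
- ρ = 0.3, SDpre = 2: SD(total) = √(3.80 + 4 + 2.34) = 3.18, power about 40%. The adjusted SD is 1.95 × √0.91 = 1.86, power about 84%.

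**5. Total stay or stay from randomisation.** Since total minus pre equals post, regressing total stay on arm and pre-randomisation days gives the same arm estimate and p-value as regressing days from randomisation to discharge on the same terms. A plain t test on days from randomisation has SD 1.95 and about 80% power at every SDpre. The two routes agree when ρ is near zero; otherwise the model is somewhat more precise.

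**6. Transformed total stay.** Pre-randomisation days add to total stay only on the raw scale. At SDpre 2, 3 and 4, simulated adjusted power was 76, 72 and 71% on logs and 74, 68 and 64% on ranks, below the raw-scale figures.

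**The case against.** The strongest reply is that nothing here is an error. Randomisation balances pre-randomisation days in expectation, the unadjusted test is valid, and its interval honestly shows the noise. The primary outcome already leaves these days out, and reporting a whole admission beside it is reasonable description. All of this stands. A reader might infer bias, or a flaw in the primary analysis; the documents support neither.

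A reader might also infer that the plan loses a promised 80% power. The SAP's "According to a two-sided type I error of 0.05 and 80% power" belongs to post-intervention stay, and no power is claimed for total stay. The 80% is only a reference point.

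It might further seem that one long-stay patient could make the result look null or reversed. An extra 35 pre-randomisation days does shift a 16-patient mean by 35/16 = 2.2 days. But the SAP offers Mann-Whitney for such data. With that patient in the shorter-stay arm, simulated power was about 0% for the t test and about 58% for Mann-Whitney; with the patient in the other arm, Mann-Whitney kept about 83%. The outlier argument is therefore weak. Mann-Whitney does not, however, remove the general loss shown in the table.

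Lastly, an adjusted total stay comes close to the primary outcome. It differs by the wait from randomisation to intervention, so it is not redundant.

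**Conclusion.** The point holds as an optional gain in precision on one secondary outcome. If total stay means admission to discharge, the unadjusted comparison carries variance that a value fixed at entry could remove.

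The size is not known. Under the stated assumptions (16 per arm, 2-day effect, SDpost 1.95, ρ = 0), the loss runs from about 2 percentage points of power at a pre-randomisation SD of 0.5 days to more than half the power at 3 days and above. A negative correlation can cancel it, and a positive one enlarges it. The documents give no figure that narrows this range.

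Two premises are inferred. The admission start is the natural reading, not a stated definition. Neither document says that admission date, randomisation date or pre-randomisation days are recorded for analysis, so it cannot be assumed that a baseline value is already in hand.

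**What to change.** - Define total stay in the protocol as admission to discharge, and list the admission and randomisation dates as data to be kept.
- Add one SAP sentence naming, in advance, one of two comparisons: a raw-scale linear model for total stay with arm and days from admission to randomisation as terms; or days from randomisation to discharge by t test, or Mann-Whitney if skewed.
- Report raw total stay by arm as description.
- Do not log- or rank-transform total stay for the adjusted model. If skewness is the worry, Mann-Whitney on days from randomisation avoids the problem.

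The cost is one definition, one sentence and, for the model, one degree of freedom. Total stay on this definition already needs the admission date, and randomisation is already day 0. Sample size, primary outcome and conduct do not change.

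### The adverse-event outcome names only two events, so other non-fatal complications of either treatment are not counted as harm and the safety comparison is incomplete

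*Protocol*

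**What the plan says.** Under Study Outcome, the Protocol's secondary measures give the adverse-event heading two entries: "Pleural bleeding defined as drop in serum hematocrit requiring blood transfusion or causing hemodynamic instability" and "Significant pain requiring escalation of analgesia". Both apply to both arms. Two neighbouring outcomes also bear on harm:

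- Mortality: "In hospital and 30 day mortality".
- Treatment failure, which includes "1-Surgical intervention (VATS, open thoracotomy) in the medical thoracoscopy or fibrinolytic therapy arm" and, by arm, an extra chest tube or added fibrinolytic therapy. It is framed by continuing signs of infection or loculation 48 hours after intervention, and its chest-tube items by lack of clinical response.

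The Operative Technique section describes what each arm is exposed to. In the thoracoscopy arm, "thoracoscopy will be performed under moderate sedation in the operating room or endoscopy suite with continuous monitoring as per standard protocols"; using forceps, "fibrinous septate will be disrupted with fluid and fibrinopurulent material aspirated and removed from the pleural cavity"; and a 24Fr drain is left on suction. In the fibrinolytic arm, a tube of 14-French or less is inserted, up to six doses of tPA and DNase are instilled, and the tube is opened to suction. Exclusion 6 (Patient Population) removes patients with "inability to tolerate procedure due to hemodynamic instability or severe hypoxemia".

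The SAP assigns Fisher's exact test to categorical variables and sets 16 patients per group. It says nothing specific about adverse events.

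**The concern.** The primary outcome is hospital stay after the intervention. If one arm goes home sooner, a reader will ask what complications that arm had. The answer comes from the adverse-event table, and a table built from these entries can show only major pleural bleeding and pain. Other non-fatal complications would not appear in it, so a patient with one could be tabulated as having had no adverse event. A report of similar safety in the two arms would then reflect the narrowness of the list as much as the treatments.

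**Working it through.** **Step 1. Where would a complication be recorded?** The table takes each kind of event through the outcomes in the Protocol's Study Outcome section. The event types are examples; apart from bleeding, pain and death, the Protocol does not name them as outcomes.

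| Event | Arm exposed | Counted as adverse event? | Any other outcome? |
|---|---|---|---|
| Respiratory event under sedation, survived | Thoracoscopy | No | Stay, if prolonged |
| Hemodynamic instability without pleural bleeding | Either | No | Stay, if prolonged |
| Air leak or new pleural air | Either; forceps work in thoracoscopy only | No | Stay, if prolonged; failure only if surgery or a tube is judged to be for non-response |
| Pleural bleeding below the threshold | Either | No | Stay, if prolonged |
| Non-pleural bleeding | Either | No | Stay, if prolonged |
| Reaction to tPA or DNase | Fibrinolytic (thoracoscopy only if given later) | No | Stay, if prolonged |
| Chest-tube complication | Either | Only through pain | Stay, if prolonged |
| Fatal complication | Either | Only if it met the bleeding or pain entry | Mortality |

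Stay and mortality register a consequence without identifying it as a complication of treatment. An event that resolves before the planned discharge leaves no trace in any outcome.

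**Step 2. Does the omission have a direction?** The documents give no event rates, so these are assumptions. Let listed events occur in b = 10% of patients in each arm, and unlisted events, independently, in x (thoracoscopy) and y (fibrinolysis). The counted difference is b - b = 0. The true difference in patients with any event, thoracoscopy minus fibrinolysis, is

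[1 - (1-b)(1-x)] - [1 - (1-b)(1-y)] = (1-b)(x-y) = 0.9(x-y).

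- x = 10%, y = 0%: +9.0 points (thoracoscopy harm hidden)
- x = 10%, y = 10%: 0
- x = 0%, y = 10%: -9.0 points (fibrinolytic harm hidden)
- x and y each from 0 to 20%: -18 to +18 points

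The sign depends on x and y, which the documents do not give.

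**Step 3. What could 16 per arm show if everything were recorded?** The plan states no figure for adverse events. Its 16 per arm (SAP, Statistical Analysis) was set for hospital stay and is taken as given.

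- Chance that an arm sees at least one event, 1 - (1-p)^16: 15% at p = 1%, 28% at 2%, 56% at 5%, 81% at 10%, 97% at 20%.
- Exact two-sided 95% upper limit for 0/16: 1 - 0.025^(1/16) = 20.6%.
- Two-sided Fisher p for k v 0, which is 2·C(16,k)/C(32,k): 3 v 0 gives 2×560/4960 = 0.23; 4 v 0 gives 2×1820/35960 = 0.101; 5 v 0 gives 2×4368/201376 = 0.043.
- Power of Fisher's test by exact enumeration, at assumed true rates: 9.9% for 20% v 5%, 31.1% for 30% v 5%, 56.5% for 40% v 5%.

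Unlisted events at rates of 5 to 10% would more likely than not occur at least once in an arm, so recording them is worthwhile. A test comparing them would rarely be informative.

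**The case against.** A reader might infer that the list favours thoracoscopy by design, because sedation and forceps work belong to that arm and their non-bleeding harms have no entry. The documents do not support that. The two entries have the same definition in both arms, and either can follow a port, a forceps procedure or a 24Fr drain as well as an instillation. Harms of the fibrinolytic arm are also missing from the list, and that arm too has a tube inserted and put on suction. Step 2 shows that the sign is open.

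A reader might also take exclusion 6 as the Protocol's admission that thoracoscopy causes hypoxemia or instability. It describes a patient's condition before entry. Lung injury is likewise an inference from the forceps step; the Protocol does not name it.

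Nor are all such harms lost to the trial. Death reaches the mortality outcome, instability from pleural bleeding meets the first entry, and a complication that delays discharge lengthens the primary outcome.

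Finally, the public text is short. It opens at the patient population with reference numbers already at 26, and the adverse-event heading carries no words that expressly close the list. The fair statement is therefore that wider collection is not specified in these documents. They do not show that it did not take place.

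These objections stand, and they remove any claim about direction. They leave the gap itself: the outcome as written names two events, and no other outcome labels a survivable complication as harm.

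**Conclusion.** The point holds as one of completeness. Followed as written, the plan counts major pleural bleeding and pain as adverse events and leaves other non-fatal complications of both treatments uncounted as harm. The safety comparison is therefore incomplete, in a direction the documents do not determine. The range of -18 to +18 points rests on assumed rates, on equal listed rates of 10% and on independence; it illustrates that the sign is open and does not estimate a bias. Widening the list would not make the trial able to test safety: 0/16 still leaves 20.6% as the upper limit, and nothing short of 5 v 0 reaches p<0.05 when one arm has no events. That limit comes from the sample size and applies with or without the change. The analysis of the primary outcome is unaffected; what is weakened is any safety statement set beside it.

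**What to change.** Keep the two existing entries and add:

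- all serious adverse events;
- any procedure- or drug-related complication that needed unplanned treatment, escalation of care, surgery or a longer stay;
- new pleural air or air leak, seen at the drain or on the CT already done before tube removal. This is a finding rather than a consequence, so it should have its own line in the table.

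Record all of these over one stated window, starting at randomization, in both arms. The 30-day mortality point and the 12-week visit are already in the Protocol and either could end it. Define events by clinical consequence and not by monitored values: continuous monitoring is specified only for thoracoscopy, so counting any recorded desaturation or pressure drop would find more events in that arm because it is watched more closely.

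Report the number of patients with any event, and with each type, by arm with exact confidence intervals. State in the SAP that this is descriptive and that a non-significant Fisher's test will not be read as equal safety.

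The cost is a few case-report fields, some attribution of complications by the investigator, and one table. The drawback is that the safety result may look less favourable in either arm.
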